6.3.4. POINT OF ENROLLMENT

Patients that sign consent will be considered a study candidate; however, he/she will only be included into the study upon meeting the inclusion and exclusion criteria detailed in Section 6.3 and the criteria listed below.

Study candidates will be considered enrolled in the study when all the criteria below have been met:

- successfully implanted with a commercially approved LivaNova Perceval bioprosthetic aortic heart valve
- all inclusion and exclusion criteria were met, and
- an informed consent was obtained (including date and signature)

The date of the enrollment will be the later of either the date the Informed Consent was signed, or the date of the implant of the valve.

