5.4 DEFINITIONS

Investigational Device (ID)	PERCEVAL (PMA P150011)
Baseline	Last non-missing observation (scheduled or unscheduled) before implant.
	Measurements collected the day of implant, in absence of other time information, are considered baseline data.
	If a subject is missing the planned baseline collection, the previous non-missing evaluation will become the baseline value.
	If any observation will be available before or on the day of implant, an unscheduled assessment done before the discharged visit can be used as baseline.
Study Day Count	The day of implant is defined as study Day 1.
	Calculate the study day according to the following rules:
	If date < study Day 1 then study day = Date – study Day 1
	If date ≥ study Day 1 then study day = Date – study Day 1 +1

LN-GLB-CLN-TEM-0033 rev1 Page 10 of 42

Study phases	
Pre-implant (Screening)	Screening and pre-implant assessments, where informed consent is signed and eligible criteria are met, before subjects will be considered enrolled in the study.
Implant (Enrollment)	During the implant until the establishment of a successful procedure.
Hospital Discharge	Before the subject is discharged or within 30 days of implant.
ACT/DAPT discontinua- tion visit	Visit required only for subjects on ACT/DAPT at hospital discharge: from 1 to 6 months (3 months preferred) postimplant.
Follow-up evaluations: First CT scan	Minimum of 30 days (+ 60 days) after discharge or discontinuation of ACT/DAPT (expected from 1 to 6 months post-implant).
Second CT scan	For subject with reduced leaflet motion previously detected by Core Lab; after the 1^{st} CT scan, but prior to 1 year follow-up visit (expected from 6 to 10 months post-implant).
1 year	Clinic visit at 1 year ± 1 month after the day of the implant.
Pre-implant period	Period from signing of the informed consent until the day before the implant.
Post-implant period	Period from successful implantation of Perceval bioprosthetic heart valve to 30-days after hospital discharge visit (for subjects discharged off ACT/DAPT) or ACT/DAPT discontinuation visit (for subjects discharged on ACT/DAPT).
Post-ACT/DAPT period	Period from 31 st day after the hospital discharge (for subjects discharged off ACT/DAPT) or 1 st day after the ACT/DAPT discontinuation (for subjects discharged on ACT/DAPT) to 1 year visit.

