6.2 ENROLLED ANALYSIS POPULATION

The "Enrolled population" (ENR) is defined as all subject who will be enrolled in the study. Subjects who signed the informed consent but do not satisfy the eligible criteria should be withdrawn from the study prior to implant and will be considered as screening failure.

Screening failures will be reordered into logs that are supplied to the sites. These logs can be collected by monitors for internal sponsor records and screen failures will be not entered into e-CRF.

All enrolled subjects will be analyzed under the Intention-To-Treat (ITT) principle, such that subjects will be analyzed according to the final implant attempt to place an aortic Perceval valve. The ENR will be used mainly for subject disposition summaries.

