13 SECONDARY SAFETY ANALYSIS

All safety data will be presented for the SAF and will be summarized descriptively by overall and, where specified, by occurrence of enrollment (subjects enrolled at implant/after implant) and/or study period (post-implant and post-ACT/DAPT).

Study: APR002 BELIEVE

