13.1.1 Adverse Events overviews

The following overview tables will be generated by overall and study period (post-implant and post-ACT/DAPT at 3, 6, 9 and 12 months post-implant as defined in Section 5.4) further stratified by enrollment occurrence (before or at implant/after implant).

- Summary of the number and percentage of subjects with at least one
 - o SAE
 - SAE by procedure relatedness
 - SAE by device relatedness
 - Device related SAE by expectedness
 - SAE leading to study termination
 - SAE leading to study termination by procedure relatedness
 - SAE leading to study termination by device relatedness
 - Device related SAE leading to study termination by expectedness
 - SAE leading to death
 - SAE leading to death by procedure relatedness
 - SAE leading to death by device relatedness
 - Device related SAE leading to death by expectedness

The percentage denominator will be the number of subjects.

- Summary of the number and percentage of SAEs for:
 - SAE
 - SAE by procedure relatedness
 - SAE by device relatedness
 - Device related SAE by expectedness
 - SAE leading to study termination
 - SAE leading to study termination by procedure relatedness
 - SAE leading to study termination by device relatedness
 - Device related SAE leading to study termination by expectedness
 - SAEs leading to death
 - SAE leading to death by procedure relatedness
 - SAE leading to death by device relatedness
 - Device related SAE leading to death by expectedness

The percentage denominator will be the total number of SAEs.

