18.13 DATA DERIVATIONS

Derived variable	Derivation algorithm based on e-CRF version 8 dated 18 th July 2017
Concomitant	"Implant Surgical Details" e-CRF:
Procedures	Group "Implanted with a concomitant procedure" if CPYN= "Yes"
	Group "Implanted without a concomitant procedure" if CPYN= "No"
Subject symptoms	"Subject Clinical Assessment" e-CRF at "at 1 Month After ACT Dx (1st CT-Scan)" or "Reduced Leaflet Visit (2nd CT-Scan)" Visits:
	Group "Asymptomatic" if SCSYMPYN = "No"
	Group "Symptomatic" if SCSYMPYN = "Yes"
ACT/DATP	"Subject Clinical Assessment" and e-CRF:
	 Group "Subject on ACT/DAPT at hospital discharged (or 30-days after implant)" if SCDISCYN= "Yes"
	Group "Subject off ACT/DAPT at hospital discharged (or 30-days after implant" if SCDISCYN= "No"
Core Lab evaluation	"Vist (at 1 Month After ACT Dx or at Reduced Leaflet)" e-CRF:
by	Group "CT scan" if IMGTYPE= "4D CT Acquisition"
	Group "TEE" if IMGTYPE = "Transesophageal Echo"
Pre-implant period	If Enrolled Date= DXSTDAT2 ("Implant Surgical Details" e-CRF) then
	Start date: ICFDAT ("Inclusion/Exclusion Criteria" e-CRF)
	End date: DXSTDAT2 -1
	If Enrolled Date= ICFDAT then
	Start date=End date= "None".

LN-GLB-CLN-TEM-0033 rev1 Page 39 of 42

Post-implant period	If DXPER= "Yes" ("Implant Surgical Details" e-CRF) Start date: DXSTDAT2, End date: if SCDISCYN= "No" ("Subject Clinical Assessment" e-CRF) then End date= VISDAT (at Hospital Discharge visit) + 30 if SCDISCYN= "Yes" ("Subject Clinical Assessment" e-CRF) then End date= VISDAT (et ACT Disceptionation visit) + 30
Post-ACT/DAPT period	 End date= VISDAT (at ACT Discontinuation visit) + 30 Start date: if SCDISCYN= "No" ("Subject Clinical Assessment" e-CRF) then Start date= VISDAT (at Hospital Discharge visit) + 31 if SCDISCYN= "Yes" ("Subject Clinical Assessment" e-CRF) then Start date= VISDAT (at ACT Discontinuation visit) + 31 End date: VISDAT (at Year 1 visit)
Implant procedure completer	 DXPERF= "Yes" ("Implant Surgical Details" e-CRF) and DSSTDAT ≥ ACTDIDAT ("Study Termination" e-CRF) + 31 o if DSSTDAT missing, last available VISDAT ≥ ACTDIDAT + 31
Study completer	DSDECOD= "Completed" ("Study Termination" e-CRF)
SCR population	ICFDAT not missing ("Inclusion/Exclusion Criteria" e-CRF)
Enrolled Date	Derived from maximum between Consent Date and Implant Date. "Inclusion/Exclusion Criteria" e-CRF and "Implant Surgical Details" e-CRF Max(ICFDAT; DXSTDAT2)

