ENR population	 SCR flag= "Yes" and DXSTDAT2 not missing ("Implant Surgical Details" e-CRF) and existing Enrolled Date
SAF population	 ENR flag= "Yes", and DXPERF= "Yes" ("Implant Surgical Details" e-CRF)
PP population	As reported in the Believe Risk Based Study Management Plan.
Time to study	"Implant Surgical Details" e-CRF and "Study Termination" e-CRF
termination (months)	[DSSTDAT – DXSTDAT2 + 1] / 30.4375

COPYRIGHT LIVANOVA. ALL RIGHTS RESERVED. MAY NOT BE REPRODUCED WITHOUT PERMISSION. ALL HARD COPIES SHOULD BE CHECKED AGAINST THE CURRENT ELECTRONIC VERSION WITHIN MASTERCONTROL PRIOR TO USE AND DESTROYED PROMPTLY THEREAFTER. ALL HARD COPIES ARE CONSIDERED UNCONTROLLED DOCUMENTS.

LN-GLB-CLN-TEM-0033 rev1 Page 40 of 42

Time to event	"Implant Surgical Details" e-CRF
(months)	[Even date – DXSTDAT2 + 1] / 30.4375 Subjects ongoing and who are free from event at the analysis cutoff date will be censored at the analysis cut-off date. Subjects who have discontinued without an event will be censored at the date of discontinuation.
Age at Enrollment (years)	"Demographics" e-CRF and "Inclusion/Exclusion Criteria" e-CRF Age= [ICFDAT - BRTHDAT + 1]/365.25 As only month and year of birth are reported in the CRF, 1 st day of the month will be used for birth date.
Change from baseline	Test Value at Visit X - Baseline Value

Where

ACTDIDAT = "Date Subject Discontinued ACT/DAPT Therapy"

BRTHDAT= "Date of Birth"

CPAETERM= "Complications/Please specify if any of the following intraoperative complications occurred. /AE Term"

CPYN= "Was concomitant procedure performed?"

DIMODEL= "Valve Model"

DSDECOD= "Reason for Termination"

DSSTDAT= "Date of Study Termination"

DVDECOD= "Deviation Description"

DVICSPEC= "If Informed Consent, specify reason"

DXPERF= "Was the implant successful?"

DXSTDAT2 = "Date of Implant"

ICFDAT = "Informed Consent Date"

IEYN= "Met All Eligibility Criteria?"

COPYRIGHT LIVANOVA. ALL RIGHTS RESERVED. MAY NOT BE REPRODUCED WITHOUT PERMISSION. ALL HARD COPIES SHOULD BE CHECKED AGAINST THE CURRENT ELECTRONIC VERSION WITHIN MASTERCONTROL PRIOR TO USE AND DESTROYED PROMPTLY THEREAFTER. ALL HARD COPIES ARE CONSIDERED UNCONTROLLED DOCUMENTS.

LN-GLB-CLN-TEM-0033 rev1 Page 41 of 42

IMGTYPE= "Specify the imaging modality currently being used for the subject"

MHCVDAT = "If Myocardial Infarction, date"

MHSTDAT3= "If Stroke, date"

NY= "No/Yes"

SCDISCYN= "Was the subject discharged on anticoagulant and/or dual platelet therapy?"

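### The SAP 11.5 Cox models start at implant but use covariates known only at the first scan visit, so earlier non-fatal events are attributed to a later finding

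*SAP*

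**What the plan says.** SAP 11.5 analyses all-cause mortality and the valve-related events by time-to-event methods, with one-by-one Cox models. SAP 18.13 gives the time variable as "Even date – DXSTDAT2 + 1] / 30.4375", counted from implant. SAP 5.2 and 18.13 give right-censoring rules only; no entry time is defined for these outcomes.

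The Cox covariates include reduced leaflet motion at the first CT scan. They also include the SAP 5.3 subgroups, of which symptom status and imaging modality (CT or TEE) are taken at the scan visit. SAP 11.5 does not say which scan applies to symptoms; SAP 11.2 uses the first. SAP 5.4 times the first scan at "Minimum of 30 days (+ 60 days) after discharge or discontinuation of ACT/DAPT (expected from 1 to 6 months post-implant"). Neither a landmark nor time-dependent coding is stated.

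On enrolment, Protocol 6.3.4 says: "The date of the enrollment will be the later of either the date the Informed Consent was signed, or the date of the implant". SAP 18.13 derives Enrolled Date the same way ("Derived from maximum between Consent Date and Implant Date"). SAP 13 reports safety, where specified, "by occurrence of enrollment (subjects enrolled at implant/after implant"), and SAP 13.1.1 has its tables "further stratified by enrollment occurrence (before or at implant/after implant"). The schedule table in Protocol 8.1 places the column containing informed consent after successful implant. A footnote allows an item to come earlier, although the damaged layout hides which one.

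Two SAP sections instead assume consent before implant. SAP 5.4 describes the pre-implant phase as "Screening and pre-implant assessments, where informed consent is signed and eligible criteria are met, before subjects will be considered enrolled in the study". SAP 6.2 says consented but ineligible subjects "should be withdrawn from the study prior to implant and will be considered as screening failure".

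**The concern.** A covariate used as fixed from time zero should be known at time zero. Here the clock starts at implant and the covariate is learned one to several months later. A bleed or stroke in the first weeks is then counted in the group defined by a scan that had not yet been done.

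For symptoms there is also circularity. SAP 11.2 lists signs of thromboembolic events among the features that make a subject symptomatic, and thromboembolic events are an 11.5 outcome.

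Freedom from valve safety events is secondary endpoint 4. A hazard ratio for reduced leaflet motion is the figure most likely to be read as the clinical consequence of the finding.

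The secondary issue is that a subject who consents after implant cannot have died before consenting. Survival counted from implant then includes a stretch in which that subject could not have failed.

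**Working it through.** **Plan's own figures.** The documents give no figure for the 11.5 analyses. The design figure reproduces: 7/75 (9.3%) has an exact 90% interval of 4.5% to 16.8%, width 12.35%, below 13%; and 75/0.85 = 88.2. Neither is in dispute. The first suggests about 7 subjects with reduced motion if the proportion stays just below 10%.

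**1. Size of the covariate error.** Let s be the share of the unexposed first-year cumulative hazard that falls before the scan. The implant-origin hazard ratio is roughly the weighted mean s × HR(pre) + (1 − s) × HR(post). A Cox simulation checks this (four runs of 60,000 per cell, 9% exposed, scan uniform on days 60–150, 10% one-year risk in the unexposed). The hazard ratio pairs, the risk and s are assumptions.

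| s | Pre 1, post 3: 3 − 2s | Simulated | Pre 3, post 1: 1 + 2s | Simulated |
|---|---|---|---|---|
| 0.1 | 2.8 | 2.73 | 1.2 | 1.20 |
| 0.2 | 2.6 | 2.53 | 1.4 | 1.42 |
| 0.4 | 2.2 | 2.16 | 1.8 | 1.85 |
| 0.6 | 1.8 | 1.78 | 2.2 | 2.31 |
| 0.8 | 1.4 | 1.41 | 2.6 | 2.66 |

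Starting at the scan gives 2.93–3.18 and 0.98–1.03, that is, 3 and 1 within simulation error.

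The documents offer little on s. Protocol 2.3.1 gives stroke as 1.2% early and 0.8% late, so 1.2/2.0 = 60% early. Major PVL is 1.4% and 0.3%, so 1.4/1.7 = 82% early. That section ties neither period to the scan.

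**2. Mortality.** Subjects who die before the scan have no scan value. SAP 18.5 does not impute missing values unless the SAP says otherwise, and the multiple imputation in SAP 10.5 is written for the primary endpoint, so on the natural reading they drop out. In a simulation with no true effect, scanned subjects analysed from implant give a hazard ratio of 1.02–1.05, the same as with entry at the scan. The effect on the mortality hazard ratio is therefore small.

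**3. Precision after correction.** With 7 exposed subjects and one-year risk r, the post-scan event probability is p = 1 − (1 − r)^(HR × post-scan share). Expected exposed events are 7p, and the chance of none is (1 − p)^7. For post-scan shares of 20% to 90%:
- r = 10%, HR 1: 0.15–0.63 events; none in 86%–52% of studies.
- r = 10%, HR 3: 0.43–1.73 events; none in 64%–14%.
- r = 2% (stroke, 1.2% + 0.8%), HR 1: 0.03–0.13 events; none in 97%–88%.

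**4. Late consent.** Assume the 3.4% early mortality of Protocol 2.3.1 falls within 30 days and the 7.0% late mortality in days 31–365. Then S(30) = 0.966 and S(365) = 0.966 × 0.93 = 0.898. With a share q consenting late, after a uniform delay u, reported survival is (1 − q) × S(365) + q × mean[S(365)/S(u)]. Bias in percentage points:

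| Delay | q = 25% | 50% | 75% | 100% |
|---|---|---|---|---|
| 0–7 days | 0.09 | 0.18 | 0.27 | 0.36 |
| 0–14 days | 0.18 | 0.36 | 0.55 | 0.73 |
| 0–30 days | 0.39 | 0.79 | 1.18 | 1.57 |

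Spreading the 7.0% over three years instead gives up to 1.65. The 90% half-width at n = 88 is 1.645 × √(0.898 × 0.102/88) = 5.3 points.

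**5. Does delayed entry help at n = 88?** In 3,000 simulated studies per cell it removes the bias, but one-year root mean squared error rises in all nine cells with q from 25% to 75%: from 3.1–3.3 points as planned to 3.2–3.6. At q = 100% and 0–30 days it rises from 3.4 to 4.9.

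**The case against.** **The models are exploratory, and events will be few.** This stands. The study is declared descriptive, and step 3 shows that most of these hazard ratios will be imprecise or inestimable however they are set up. It limits severity but does not justify attributing events to later findings.

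**The proportional-hazards check would catch it.** Protocol 10.1.2 and SAP 11.5 plan such a check, and a hazard ratio that changes at the scan is non-proportional. But power would be low here. The Weibull fallback keeps the same covariates and origin and is itself a proportional-hazards form, so it does not correct the order of events and findings.

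**The scan dates detection, not onset.** Fair: reduced motion may precede the scan, so the post-scan hazard ratio is a choice of estimand. Onset is not observed, however, and a covariate defined at the scan can support a prognostic reading only for what follows it.

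**Late enrolment is already partly visible.** SAP 13.1.1 and 13.1.2 tabulate SAEs leading to death by enrolment occurrence, and linearized rates start on day 31. This stands, and it is one reason to treat late consent as secondary.

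A reader might infer that the mortality hazard ratio is badly distorted. With no true effect it would read 0.38–0.59 if unscanned subjects were coded as free of reduced motion, but no section says they will be. A reader might also infer that the planned Kaplan-Meier curve must be replaced. The share and delay of late consent are undocumented, two SAP sections take consent before implant as the default (with no bias in that case), and step 5 shows that delayed entry costs more precision than the bias it removes.

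**Conclusion.** The Cox models in SAP 11.5 are wrong as written for the three scan-visit covariates, chiefly for non-fatal outcomes. The hazard ratio can err in either direction: under the assumed scenarios a post-scan value of 3 reads anywhere from about 2.7 down to 1.4, and a null post-scan effect from about 1.2 up to 2.7. The hazard ratio pairs and the 10% one-year risk are illustrative, and the share of events before the scan is not documented.

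Late consent is a secondary point. The bias is upward, from zero if everyone consents by implant to about 1.6 points at one year if all consent late over 0–30 days. That is well inside the 5.3-point half-width. It rests on the assumed mortality split and delays; the documents state no maximum delay, and longer ones would increase it.

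The primary endpoint, its interval and the sample size are unaffected. The separate Kaplan-Meier analysis in 11.5 that enters subjects when ACT/DAPT stops is not part of this point. Severity: minor.

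**What to change.** In SAP 11.5, for reduced leaflet motion, symptom status and imaging modality at the first scan visit:
- Start follow-up at the scan date in scanned subjects and count only later events, or code the covariate as time-dependent.
- State that unscanned subjects are not coded as 'No'.
- Report event counts by group, and give a hazard ratio only where it can be estimated.

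For late consent:
- Keep the planned implant-origin Kaplan-Meier analysis.
- Report 11.5 all-cause mortality by enrolment occurrence, as SAP 13 does for SAEs.
- Add delayed entry at Enrolled Date as a sensitivity analysis for all-cause mortality only.
- Reconcile the consent timing in Protocol 6.3.4, the Protocol 8.1 schedule and SAP 13, 13.1.1 and 18.13 with that in SAP 5.4 and 6.2.

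The cost is SAP wording and programming on dates already collected. The downsides are few post-scan events, so that many hazard ratios will not be reported, and wider early intervals in the sensitivity analysis. Delayed entry also cannot recover patients who died before they could consent.
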